- Constitutional symptoms: headache, feeling feverish, body aches and pains, and fatigue
- Systemic symptoms: headache, feeling feverish, body aches and pains, fatigue, neck pain, interrupted sleep, and loss of appetite
- Total score: all items in Domain 1

Descriptive statistics of actual value and change from baseline for average score in each scale will be presented by treatment group at each visit.

If there are missing values in items in Domain 1, missing data will be handled according to section 10.3.

- Descriptive analysis for AUC of average symptom score from date of baseline assessment to last measurable value of subjects who have at least one post-baseline result.

If there are missing values in average symptom scores between observed ones, the missing values are assumed to fall linearly between observed values.

- Mean daily symptom score on the Domain 1 of the Flu-iiQ™

Average of total symptom score for each time point will be plotted with the SD of mean score.

- Incidence of symptoms on the Domain 1 with Grade 2 or Higher

The proportion of subjects who developed any of the 7 individual influenza symptoms (cough, sore throat, nasal congestion, headache, feeling feverish, body aches and pains, and fatigue from Flu-iiQ™ Domain 1) with moderately or severe in intensity (Grade 2 or higher) will be calculated from baseline to Day 8. Most severe score will be counted per each day. Subjects with incomplete data and no recorded symptoms will not be counted (i.e. did not experience symptoms Grade 2 or higher).

All item scores of Flu-iiQ™ will be listed by each domain and time point. Additional listing for Flu-iiQ™ will be provided including average score of Domain 1 (respiratory, constitutional, systemic, total symptom score), Domain 3, Domain 4 and AUC of Domain 1.

- Viral shedding in nasopharyngeal swab samples

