Viral shedding (titers) of swab samples based on qPCR and cell culture will be evaluated at the scheduled collection times. The listing will include titer results, whether the influenza A is confirmed and Area under the Curve (AUC) of viral loads. However, since cell culture results have information of both influenza A and B, the listing and tables for cell culture will present analysis results regardless of influenza type. Changes in viral shedding will be assessed as the change from baseline in \log_{10} vp/mL and \log_{10} TCID₅₀/mL for qPCR and cell culture respectively. If viral loads are lower than LLoQ (2.18 for qPCR), they will be treated as value without inequality sign. Whereas viral load lower than LLoQ for cell culture (0.75) will be considered as negative value and a negative value will be treated as 0. If the subtype of influenza A is "H1", "NA" or "Unknown", the virus titer from HA assay will be used for cell culture analysis. Otherwise, if the subtype is "H3", the virus titer from NP ELISA will be used.

These will be summarized for each treatment group and collection time.

The following analyses will also be performed:

- Summary of viral shedding results; percentage of subjects with positive/negative viral shedding at each visit (baseline, day 2, 3, 5, 8)
- Duration (in days) of viral shedding; from date/time of baseline assessment to last positive sample. Subjects with at least one positive sample after baseline will be included in the summary.

Statistical Analysis Plan

- AUC of viral levels; from date of baseline assessment to last measurable value of subjects who have at least one post-baseline result (including BLQ (Below the Limit of Quantification) and negative values). If there are BLQ or missing values between measurable values, they are assumed to fall linearly between measurable values.
- Change from baseline in descriptive statistics of viral shedding of Swab Samples; descriptive statistics of actual value and change from baseline for viral shedding of swab samples will be presented by treatment group at each visit.
- Mean viral load titer (log values)
Mean viral load titer for each scheduled time point will be plotted with the SD of mean value.

- Incidence of secondary complications of influenza

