10.3 Missing Data Handling

10.3.1 Missing Data Handling for Primary Efficacy Analysis

When the Flu-iiQ™ has missing values (unanswered questions), two different approaches to handle the missing data will be taken to evaluate the impact of missing data on the primary efficacy results.

- 1) Missing data will not be imputed and only recorded Flu-iiQ™ will be used for the analysis.

CONFIDENTIAL

21/62 page

Effective Date: 01-Aug-2018

Statistical Analysis Plan

- 2) On the other hand, missing data will be replaced by 0 or imputed using multiple imputation when at least one score on respiratory or constitutional symptoms in Domain 1 had been recorded.

Primary efficacy results from two different approaches will be compared to assess impact of missing imputation.

Prior to missing imputation, the number of missing values on a particular scale (respiratory or constitutional symptoms in Domain 1) will be considered in determining of way of imputation as follows:

2-1) If the number of missing items is less than half of the total number of items on a scale, missing values will be replaced by 0.

- a. Respiratory symptom scale: if one of three items is missing, the other two recorded items will be used assuming a missing item has 0 value.
- b. Constitutional symptom scale: if one of four items is missing, the other three recorded items will be used assuming a missing item has 0 value.

2-2) If the number of missing items is greater than or equal to half of the total number of items on a scale, multiple imputation will be conducted unless there is evidence that missing values would have 0 value.

2-2-1) Missing items are replaced by zero: when Flu-iiQ™ is not complete, then reason of not done recorded in eCRF will be manually reviewed. If subjects had indicated that they had ceased to complete the questionnaire because their symptom had disappeared or completed the questionnaire only on days when they experienced symptoms, missing items since then will be replaced by zero.

2-2-2) Multiple imputation: for any other cases, missing data will be imputed using multiple imputation method assuming Missing at Random (MAR). Several imputed datasets created by multiple imputations will be pooled.

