10.3.2.4 Severity of Symptoms as Recorded on the Flu-iiQ™

If the number of missing items on each scale of Domain 1 is less than half of the total number of items on the scale, only the recorded items are used for the analysis. Otherwise, data of that visit will be excluded from the analysis.

10.3.2.5 Quality of Life Measures as Reported in Domain 3 and Domain 4 of the Flu-iiQ™

The same rule as described in section 10.3.2.4 will be applied.

11. Exploratory Analysis

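### The symptom and viral AUCs stop at each subject's own last measurable value, so leaving early while still ill or shedding gives a smaller total

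*SAP*

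**What the plan says.** SAP 10.2 specifies two AUCs. Under severity of symptoms it plans a "Descriptive analysis for AUC of average symptom score from date of baseline assessment to last measurable value", for subjects with at least one post-baseline result. Under viral shedding it plans "AUC of viral levels; from date of baseline assessment to last measurable value of subjects who have at least one post-baseline result", where BLQ and negative results count towards inclusion.

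The gap rules work only between two values. For symptoms: "If there are missing values in average symptom scores between observed ones, the missing values are assumed to fall linearly between observed values". For virus: "If there are BLQ or missing values between measurable values, they are assumed to fall linearly between measurable values". Neither covers what comes after the last value.

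The missing-data sections do not supply the rule. SAP 10.3.2.4, on symptom severity, uses the recorded items when fewer than half are missing on a scale. Failing that, "Otherwise, data of that visit will be excluded from the analysis". SAP 10.3.1 does separate subjects who stopped the diary because they were well (rule 2-2-1: "missing items since then will be replaced by zero") from the rest, who are multiply imputed under MAR (rule 2-2-2). That section is written for the primary endpoint. SAP 13 does not mention the AUCs.

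SAP 10.2 also assigns values to low viral results. For qPCR: "If viral loads are lower than LLoQ (2.18 for qPCR), they will be treated as value without inequality sign". A culture result below 0.75 "will be considered as negative value and a negative value will be treated as 0".

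**The concern.** An AUC that is a total over a window chosen by the subject's own follow-up mixes two things: how ill the subject was, and how long the subject was observed. Lost time enters as zero burden. The error runs one way, because missing follow-up can never raise the AUC.

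The viral AUC has a second difficulty. The SAP does not define *measurable*, but its gap rule sets BLQ and measurable values against each other. If the word means quantifiable, observed BLQ or negative swabs at the end of the series are cut as well. A subject who cleared virus and one lost while shedding can then receive the same AUC.

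What is at stake is the reading of these summaries across arms. Each AUC has its own ITT and ITTI tables in SAP 14.7. Protocol 2.2 bases the study partly on earlier trends in viral shedding and total symptom scores, and says efficacy information will feed dose selection.

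**Working it through.** **Inputs from the documents.** Day 3 is 48 h and Day 8 is 168 h after the start of infusion; swabs are taken at screening and at 24, 48, 96 and 168 h; the diary is completed twice daily from Day 1 to Day 8 (SAP 14.1). Symptoms score 0 to 3 (SAP 10.1). The qPCR LLoQ is 2.18 and the culture LLoQ 0.75 (SAP 10.2). The plan gives no figure for either AUC. Its only nearby figure is 10% dropout (SAP 5.2), which reproduces: 164/0.90 = 182.2, rounded up to 183. That 10% is not tied to the diary period.

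**Assumptions.** All score and titer profiles, and the share of subjects stopping, are illustrative. Baseline is placed at time 0, so Day 8 is t = 7 days.

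**Step 1: direction.** AUC = Σ (yᵢ + yᵢ₊₁)/2 × Δt. Every counted y is at least 0, so ending the sum early lowers the AUC or leaves it unchanged.

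**Step 2: one subject's symptom AUC.** Score falls from 2.0 to 0.2 over 7 days.

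- Linear: y(t) = 2.0 − (1.8/7)t, so y(2) = 1.486 and y(3) = 1.229.
  - Full: (2.0 + 0.2)/2 × 7 = 7.70.
  - To 48 h: (2.0 + 1.486)/2 × 2 = 3.49, and 1 − 3.49/7.70 = 55% lower.
  - To 3 elapsed days: (2.0 + 1.229)/2 × 3 = 4.84, and 1 − 4.84/7.70 = 37% lower.
- Exponential: y(t) = 2.0 × 10^(−t/7). The share retained at s days is (1 − 10^(−s/7))/(1 − 0.1).
  - To 48 h: (1 − 0.518)/0.9 = 0.536, or 46% lower.
  - To 3 elapsed days: (1 − 0.373)/0.9 = 0.697, or 30% lower.

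Other shapes starting at 2 and stopped at 48 h: linear to 0 at Day 8 gives 3.43 against 7.00 (49% retained); a 2-day half-life gives 2.89 against 5.27 (55%); a constant 2 gives 4.00 against 14.00 (29%).

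**Step 3: the arm mean.** If a share f stops at 48 h and stoppers follow the same profile as the rest, the mean falls by f × (loss per stopper). With f = 10%: 0.10 × 55% = 5.5% (linear) and 0.10 × 46% = 4.6% (exponential), so about 5%. Across the other three shapes the range is 4.5% to 7.1%.

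**Step 4: a stopper who is already well.** A score falling from 2.0 to 0 by 3 days gives (2.0 + 0)/2 × 3 = 3.0, whether or not the later zeros are recorded. Nothing is lost.

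**Step 5: viral AUC, qPCR.** Assumed log10 titers are 6, 5, 4 at t = 0, 1, 2, with later swabs at t = 4 and 7.

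| Subject | Calculation | AUC |
|---|---|---|
| Lost after Day 3 while shedding | 5.5 + 4.5 | 10.0 |
| BLQ on Days 5 and 8, cut at last quantifiable value | 5.5 + 4.5 | 10.0 |
| Same subject, BLQ kept at 2.18 | 10.0 + (4 + 2.18)/2 × 2 + 2.18 × 3 | 22.7 |
| Shedder with 3.5 on Day 5 and 2.5 on Day 8 | 10.0 + 7.5 + 9.0 | 26.5 |

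**Step 6: would dividing by observed time repair it?** On the linear profile the full-window average is 7.70/7 = 1.10. Stopping at 48 h gives 3.49/2 = 1.74, and at 3 days 4.84/3 = 1.61. The early stopper now looks worse than the completer, so the bias is reversed.

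**The case against.** The strongest reply is that little depends on these numbers. The protocol endpoints are severity of symptoms and viral shedding; each AUC is one of several summaries of them, labelled descriptive, with no test planned. The primary analysis has its own censoring and missing-data rules. That stands, and it limits the weight of the point.

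The reach is also narrower than the wording suggests. Completers already have a symptom window of about Day 8, because the diary ends there, suspicious-ADE diary records are added only for time-to-event analyses (SAP 10.2), and unscheduled results are generally kept out of summary tables (SAP 5.1). Staff review the diaries at visits (Protocol 6.1.1). Subjects whose remaining scores would be zero lose nothing. This too stands; the defect concerns those who stop while symptomatic or shedding.

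A reader might infer that the plan makes clearance and loss to follow-up indistinguishable. The documents do not support that in general. It can hold for the viral AUC figure, and only if *measurable* means quantifiable. The planned positive/negative percentages by visit, titers by visit and listings would still show the difference.

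A reader might also infer that the AUCs will favour CT-P27. Nothing in the documents shows that stopping will differ by arm. Equal stopping still understates the burden and blurs the comparison, but does not by itself favour one arm.

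What the reply does not supply is a rule. No section fixes the end day or says what happens after the last record. The SAP already uses a fixed baseline-to-Day-8 window for the incidence of Grade 2 or higher symptoms, in the same part of 10.2.

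**Conclusion.** The point holds as a defect in the definition of two descriptive secondary summaries. Followed as written, SAP 10.2 gives a subject who stops while symptomatic or shedding a smaller, better-looking AUC. On a fall from 2.0 to 0.2 the loss is 46% to 55% for a stop at 48 h and 30% to 37% for a stop at 3 elapsed days. An arm's mean falls by about 5% if 10% of it stops at 48 h. These sizes rest on assumed profiles and an assumed stopping share; the direction follows from the non-negative values alone. Bias between arms requires stopping to differ in share, timing or severity. The primary endpoint and type I error are unaffected.

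**What to change.** Compute both AUCs over one window, baseline to Day 8 (168 h).

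- **Symptoms.** Fill trailing scores with zero only where the eCRF reason shows the diary stopped because symptoms had gone (10.3.1, rule 2-2-1). Handle other trailing gaps by the multiple imputation under MAR of rule 2-2-2. Section 10.3.1 makes its imputation conditional on at least one recorded respiratory or constitutional score, so the text should say that the extension covers wholly blank diary entries. Add a completers-only sensitivity summary. Do not divide by observed time (Step 6).
- **Virus.** Define *measurable*. Keep observed BLQ and negative samples through Day 8 at the values SAP 10.2 assigns, and say how this fits with the interpolation rule for BLQ between measurable values. Impute missing trailing swabs, or summarise those subjects separately. Report the number per arm without a Day 8 sample.

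The cost is SAP wording and some extra programming; no new data are needed. There is one statistical price. Counting qPCR BLQ at 2.18 narrows the contrast between clearers and shedders: in Step 5, 22.7 against 26.5, rather than 10.0 against 26.5.

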4.3.1 Inclusion Criteria

Each subject must meet all the following criteria to participate in this study:

1. Subject is a male or female and aged 19 to 64 years, inclusive.
2. Subject can voluntarily provide a written informed consent.

3. Onset of illness no more than 48 hours prior to the planned administration of study drug. If the adjustments of visit schedule is required, additional 12 hours can be allowed (Maximum onset of illness: 60 hours).

Note: time of onset of illness is defined as the earlier of either (a) the time when the body temperature was first measured as $\geq 38.0^{\circ}\text{C}$ ($\geq 100.4^{\circ}\text{F}$) or (b) the time when the subject experienced the presence of at least two symptoms that are respiratory and/or constitutional (moderate to severe in intensity).

4. As reported by the subject and recorded on the Flu-iiQ™ completed at screening, the subject has at least two of the following symptoms (moderate to severe in intensity):
 - a) Respiratory symptom (cough, sore throat, or nasal congestion) or
 - b) Constitutional symptom (headache, feeling feverish, body aches and pains, or fatigue).
5. Subject has a fever $\geq 38.0^{\circ}\text{C}$ or $\geq 100.4^{\circ}\text{F}$ at screening or a history of fever within the 24 hours prior to screening and has received treatment with an antipyretic(s) in the 6 hours prior to screening.
6. Subject is diagnosed with influenza A at screening, using the Sponsor-supplied or agreed in advance rapid influenza diagnostic test. And if there is available test result confirmed as influenza A prior to obtaining written informed consent and that result was from the influenza diagnostic test which is agreed with Sponsor in advance, that test result can be allowed
7. For both male and female subjects, the subject and his/her partner (if of childbearing potential) agree to use a highly effective method of contraception during the study and for 5 months after the administration of study drug.
 - a) Male and female subjects and their partner who have been surgically sterilized for less than 6 months prior to the date of informed consent must agree to use a highly effective method of contraception during the study and for 5 months after the administration of study drug.
 - b) Menopausal females must have experienced their last menstrual period more than 12 months prior to the date of informed consent to be classified as not of childbearing potential.

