5.1 General Analysis Considerations

The statistical analysis will be performed using [REDACTED]. Any deviations from the planned analysis as described in this SAP will be justified and recorded in the CSR.

The data documented and the clinical parameters measured in this study will be described using descriptive statistics (including number [n], mean, median, Standard Deviation (SD), minimum, and maximum) for continuous variables: minimum and maximum will be presented to the same number of decimal places as the raw data, mean and median will be presented to one more decimal place than the raw data, and SD will be presented to two more decimal places than the raw data. If the geometric mean is to be presented, it will be set to the same precision as the mean. However, geometric mean will not be calculated when minimum value from the data is zero. Percent Coefficient of Variation (CV%) will be presented to two decimal places. P-values will be rounded to three decimal places. If a p-value is less than 0.001 it will be reported as "<0.001". If a p-value is greater than 0.999 it will be reported as ">0.999".

Categorical data will be summarized using count and percentage in each category. Percentages will be presented to one decimal place. The percentage will be suppressed when the count is zero in order to draw attention to the non-zero counts. "Not done" and "Missing" category will be included to account for cases of no assessment and missing respectively even if they are not recorded in eCRF. The denominator for all percentages will be the number of subjects within the treatment group for the population of interest, unless otherwise indicated.

All data will be displayed in listings. Unless otherwise specified, listings will be sorted by the treatment group, subject number, and assessment date or visit date, if applicable. In cases where more ordering is required, other variables will be included in the sort order as applicable.

Baseline will be the latest available measurement prior to the start of the infusion of study drug.

When summarizing End-of-Study (EOS) visit, the early termination cases are excluded from the summary for EOS visit, but will be presented in data listings. Unscheduled results will not be included in the summary tables except for determining baseline or if unscheduled results are necessary to interpret data, but they will be presented in data listings.

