14.3.2.5	Safety	TEAE due to Infusion Related/Anaphylactic Reactions: Additional Information (Signs & Symptoms)
16.2.8.1	Safety	Hematology
16.2.8.2	Safety	Biochemistry
16.2.8.3	Safety	Urinalysis - Numeric Parameters

CONFIDENTIAL

59/62 page

Effective Date: 01-Aug-2018

Statistical Analysis Plan

16.2.8.4	Safety	Urinalysis - Categorical Parameters
16.2.8.5	Safety	Urinalysis - Microscopic Examination
16.2.9.1	Safety	Vital Signs and Body Temperature
16.2.9.2	Safety	Immediate Hypersensitivity - Vital Signs and Body Temperature
16.2.9.3	Safety	Immediate Hypersensitivity - Electrocardiograms
16.2.9.4	Safety	12-Lead Electrocardiograms
16.2.9.5	Safety	Physical Examination and Weight
16.2.9.6	Safety	Pregnancy Test
16.2.9.7	Safety	Chest X-ray
16.2.10.1	ITT	General Comments

List of Figures

Figure Number	Population	Figure Description	Source Listing
14.2.1	ITTI	Summary of Time to Resolution of Influenza Symptom and Fever (Kaplan-Meier Plot)	Listing 16.2.5.1 Study Drug Administration, Listing 16.2.6.1 Flu-iiQ, Listing 16.2.6.2 Body Temperature from Diary
14.2.8.1.1	ITT	Mean (+/-SD) Daily Total Symptoms Score	Listing 16.2.6.1.1 Flu-iiQ: Average Score and AUC
14.2.8.1.2	ITTI	Mean (+/-SD) Daily Total Symptoms Score	Listing 16.2.6.1.1 Flu-iiQ: Average Score and AUC
14.2.8.2.1	ITT	Incidence of Symptoms Grade 2 or Higher from Baseline to Day 8	Listing 16.2.6.1 Flu-iiQ
14.2.8.2.2	ITTI	Incidence of Symptoms Grade 2 or Higher from Baseline to Day 8	Listing 16.2.6.1 Flu-iiQ

CONFIDENTIAL

60/62 page

Effective Date: 01-Aug-2018

Statistical Analysis Plan

14.2.13.1.1	ITT	Mean (+/-SD) Viral Load Titer (log values) from qPCR	Listing 16.2.6.3.1 Virus Titer Results from qPCR
14.2.13.1.2	ITTI	Mean (+/-SD) Viral Load Titer (log values) from qPCR	Listing 16.2.6.3.1 Virus Titer Results from qPCR
14.2.13.2.1	ITT	Mean (+/-SD) Viral Load Titre (log values) from Cell Culture	Listing 16.2.6.3.2 Virus Titer Results from Cell Culture
14.2.13.2.2	ITTI	Mean (+/-SD) Viral Load Titre (log values) from Cell Culture	Listing 16.2.6.3.2 Virus Titer Results from Cell Culture
14.2.18.1	PK	Mean (+/-SD) Serum Concentrations-Time Profiles of CT-P22	Listing 16.2.6.6.1 Individual Serum Concentration ($\mu\text{g}/\text{mL}$) of CT-P22
14.2.18.2	PK	Mean (+/-SD) Serum Concentrations-Time Profiles of CT-P23	Listing 16.2.6.6.2 Individual Serum Concentration ($\mu\text{g}/\text{mL}$) of CT-P23

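### On the per-day reading, the Grade 2+ symptom incidence figures report missing diary data as absence of symptoms, so the plotted proportion is p(1−m) rather than p

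*SAP*

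**What the plan says.** SAP 10.2, among the Domain 1 severity summaries, defines an incidence of Grade 2 or higher: the proportion of subjects with any of seven Flu-iiQ symptoms (three respiratory, four constitutional) rated moderate or severe, from baseline to Day 8. Three statements govern the calculation.

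- Unit of counting: "Most severe score will be counted per each day".
- Missing data: "Subjects with incomplete data and no recorded symptoms will not be counted (i.e. did not experience symptoms Grade 2 or higher".
- Denominator, from the general rule in SAP 5.1: "The denominator for all percentages will be the number of subjects within the treatment group for the population of interest, unless otherwise indicated". SAP 10.2 names no other denominator for this output.

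The output is two figures in SAP 14.7, 14.2.8.2.1 (ITT) and 14.2.8.2.2 (ITTI), titled "Incidence of Symptoms Grade 2 or Higher from Baseline to Day 8". No test is attached to them.

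Elsewhere the SAP treats missing Domain 1 data differently. For the scale scores, 10.2 says "If there are missing values in items in Domain 1, missing data will be handled according to section 10.3". There, 10.3.2.4 uses the recorded items when fewer than half on a scale are missing; beyond that, "Otherwise, data of that visit will be excluded from the analysis". For the primary endpoint, the second approach in 10.3.1 (rule 2-2), which applies once at least half of a scale is missing, uses zero only if the reason on file shows that symptoms had gone or that the diary was kept only on symptomatic days. Other cases are multiply imputed.

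**The concern.** The explanatory clause in the missing-data rule turns an unknown outcome into a negative one. A daily curve built this way falls when symptoms resolve, and it also falls when diaries stop. The figure cannot separate the two, and no display of the number missing is specified for it. If one arm has more missing entries than another, the arms separate even when incidence is the same among subjects with data, and the arm with more missing data looks better.

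Absence of symptoms is also not an obvious default soon after dosing. Protocol 4.3.1 admits a subject only if "the subject has at least two of the following symptoms (moderate to severe in intensity"), so anyone whose diary stops early was last known to be symptomatic. In the primary analysis (SAP 10.1) a subject with no diary record after dosing is censored at the start of study drug, so the outcome is treated as unknown. In these figures the same subject would appear free of Grade 2+ symptoms on each day after baseline.

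**Working it through.** The documents give no incidence and no diary-missingness rate, so there is no planned figure to reproduce. The check is algebraic, with illustrative values labelled as assumptions.

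**Definitions, for one arm on one day**

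- m = share of subjects whom the rule covers (incomplete data, no recorded symptom). Partly blank diaries are included as well as wholly blank ones.
- p = incidence of Grade 2+ among the remaining subjects.
- q = true, unseen incidence among the share m.

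**What each choice reports**

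- Rule as written with the 5.1 denominator: p(1−m) + 0 × m = p(1−m)
- Subjects with data only: p
- Every missing subject counted as an event (upper bound): p(1−m) + m
- Truth: p(1−m) + qm

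The rule therefore falls short of the truth by qm. If missingness is unrelated to symptoms, q = p and the shortfall is p × m. If every blank reflects resolved symptoms, q = 0 and the shortfall is zero. If every missing subject is symptomatic, q = 1 and the shortfall is m.

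**Two arms with the same incidence (assumed p = 50%; m = 5% versus 15%)**

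- First arm: 0.50 × 0.95 = 47.5%
- Second arm: 0.50 × 0.85 = 42.5%
- Apparent difference: 5 points in favour of the arm with more missing data.
- Shortfall from the truth: 0 to 5 points in the first arm (2.5 if unrelated) and 0 to 15 points in the second (7.5 if unrelated).

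With equal m in both arms, both proportions shrink by the same factor. At m = 10% each, 50% becomes 45% in both.

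**In counts.** Take 63 subjects (the eligible infected number planned per CT-P27 arm in SAP 5.2) and assume 6 missing and 28 events:

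- Rule as written: 28/63 = 44.4%
- Subjects with data: 28/57 = 49.1%
- All missing as events: 34/63 = 54.0%

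**If one cumulative proportion including baseline were meant.** Eligibility already requires two moderate or severe symptoms on the screening questionnaire. Nearly every subject would count from baseline, and later blanks could hardly lower the figure. The effect above exists only on the per-day reading.

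**Comparison with the other rules.** Take an entry with all three respiratory and all four constitutional items blank and no reason recorded. Under 10.3.2.4 it leaves the severity analysis. Under rule 2-2 of 10.3.1 it would not be set to zero without a supporting reason. Under the incidence rule it is no Grade 2+.

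**The case against.** **The denominator is inferred.** Not being counted could mean removal from the calculation, and that could be the exception SAP 5.1 allows for. This is a fair reading of the phrase alone. The clause that follows it, which says what not counting means, points to a non-event, and no separate denominator is named. If removal was intended, the sentence still needs correcting.

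**Per day is not stated outright.** True. The instruction to take the worst score each day supports it, and a cumulative proportion would be close to 100% by eligibility and so uninformative, but the SAP does not settle it.

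**Many blanks may be genuine zeros.** This objection has the most force. SAP 10.3.1 foresees subjects who stop the diary because symptoms have gone. For them the rule is right, and an observed-data denominator would overstate incidence. A reader might infer that the bias always equals incidence times proportion missing; the documents do not support that, because it requires missingness unrelated to symptoms. The answer is to use the recorded reason, which the primary analysis already reviews.

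**SAP 5.1 provides Missing and Not done categories.** These might show the missing share, but it is unclear that they reach a figure of proportions, and the specific rule in 10.2 assigns these subjects to the negative category.

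**The effect may be small.** The diary runs eight days with two entries a day, staff review it at visits (Protocol 6.1.1), and the trial is double-blind. Nothing in the documents predicts an imbalance in missing entries. With 63 and 38 subjects and p = 50%, the standard error of a difference is √(0.25/63 + 0.25/38) ≈ 10.3 points, so the 5-point artefact is about half of one standard error. All item scores are listed, so a reader of the report could recompute. These points limit the consequence; they do not make the rule correct.

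**Conclusion.** The point holds in a limited form. As written, and read per day with the default denominator, the rule makes the incidence figures show p(1−m) in place of the incidence p among subjects with data. At an assumed 50% incidence, missing shares of 5% and 15% produce 47.5% and 42.5%. The departure from the true incidence is qm: zero if blanks reflect resolved symptoms, p × m if missingness is unrelated to symptoms, at most m.

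Three stronger inferences are not supported:

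- That the figures will favour CT-P27. Nothing says which arm will have more missing entries.
- That the SAP otherwise never sets missing items to zero. Rule 2-1 of 10.3.1 does so when fewer than half of a scale is missing; the conflict with 10.3.1 concerns the case of half or more.
- That an efficacy conclusion is at risk. The output is descriptive, has no planned test, and sits beside other severity summaries; the primary endpoint has its own missing-data rules.

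The text should still be changed, because it prescribes an answer that other parts of the SAP avoid for the same questionnaire data, and the correction is nearly free.

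**What to change.** In SAP 10.2, replace the missing-data sentence for this output with text that does four things.

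1. States that the proportion is calculated separately for each day.
2. Sets the daily denominator as subjects who either have a recorded Grade 2+ symptom that day or have enough Domain 1 data that day under the half-items rule of 10.3.2.4.
3. Counts any other blank or incomplete day as no Grade 2+ only where the recorded reason meets 10.3.1 (2-2-1). Remaining subjects are missing for that day.
4. Prints the denominator and the number missing under each figure, by arm and day.

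The cost is a few sentences, a changed denominator in two figures, and use of reasons already in the eCRF. No new data are collected. The downside is small: the denominator varies by day, so successive points do not describe exactly the same subjects. With n and the number missing printed, a reader can work out the lower bound (all missing as non-events) and the upper bound (all missing as events).
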